3. STUDY DESIGN

Study design: Single-center, single-blind, randomized controlled trial

Primary outcome:

1. Change in the average daily GERD symptom severity score from baseline to the last week of the study in the expanded vs. standard group. GERD symptom severity is based on the sum of scores assessing the severity of daytime heartburn, nighttime heartburn, and acid reflux each on a 0-4 point scale (none, mild, moderate, severe, very severe; higher scores signify worse symptoms).

Secondary outcomes:

1. Ratio of the sum of positive correlations over the sum of negative correlations in GSR (or HRV) across patient-provider encounters for standard vs. expanded visit types and for responders vs. non-responders (those with a 50% or greater improvement in their GERD symptom severity).
2. Absolute change in GSR (or high frequency HRV signal) in patient recordings from the beginning of the study visit to the end of the study visit and correlation with subsequent change in GERD symptom severity.
3. Differences in blinded ratings of 2 minute thin slices of study visit videos from the beginning to the end of the study in supportive global impressions (e.g., engagement, relaxed, patient seems pleased/satisfied) and non-verbal behaviors (e.g., smiling) between standard and expanded visit types and correlation with subsequent change in GERD symptom severity.

Study population:

Men and women age 24-70 with heartburn symptoms 3 or more days per week not responsive to proton pump inhibitors or with known functional heartburn. We will enroll until we reach 60 completing subjects.

Study location:

University of California Davis Medical Center

Length of subject participation: 8 weeks

Length of study enrollment: 2 years

Groups:

- 1) Standard visit (n=30), modeled after an empathic, high quality conventional primary care visit.
- 2) Expanded visit (n=30), modeled after a visit with an integrative medicine provider

Randomization:

The randomization code will be generated by the study statistician as described below (sections 4.3 and 9.2). The study will be single-blinded (study providers and the research team will know what the subject is receiving but the subject will not). Randomization will be stratified based on study provider. We anticipate 5 or 6 providers each seeing 10-12 subjects (5-6 standard visits, 5-6 expanded visits).

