Each study provider will participate in an orientation session to learn how to deliver the standard and expanded visit interventions. Providers will be explicitly instructed not to offer lifestyle treatment advice for GERD to maintain uniformity of the intervention across providers. The study PI will review video recordings of the interactions to offer feedback to study providers and ensure protocol fidelity. As each study provider finishes his/her portion of the study, the PI will interview them to understand their experiences of the study, the two visit types, and their views on the doctor-patient relationship.

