6.2.4 Blinding

This is a single-blinded study. Subjects will be unaware of the possibility for two different types of study visits. Study providers and staff will be aware of the study intervention delivered, but only immediately prior to the study visit to decrease the potential for introducing bias in how study staff interact with subjects during recruitment and consent. Subjects will be debriefed at the end of the Visit 2 regarding the nature of the study and the intervention that they

received. Data will be analyzed in a blinded fashion, also to avoid introducing bias. Given the low-risk nature of the study, we do not anticipate a need to break the blind while a subject is enrolled.

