9.3 Definition of Populations

For analyses including the intervention group type, we will analyze our data according to which visit intervention subjects received (standard or expanded). We do not anticipate any discrepancies between what subjects were assigned to receive by randomization and what they actually received. Study visit type will be guided by a written script that the providers will follow during the visit. The actual intervention received will also be verified by reviewing study video recordings.

The intent to treat analysis will include all randomized subjects who received a study visit intervention. The per protocol analysis will include all individuals who received a study visit intervention and completed the follow-up questionnaires at 8

weeks.

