9.4 Interim Analyses and Stopping Rules

No interim analyses are planned. The study PI will periodically review video recordings of visit interventions as the study progresses to offer feedback to the study intervention providers and ensure adherence to the protocol.

If at any point 20% or more of participants have dropped from the study due to adverse effects from amitriptyline or omeprazole and/or there is a serious adverse event likely due to amitriptyline or omeprazole, the study team will meet with the study safety monitor to determine whether any protocol modifications are necessary.

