9.5.2 Secondary Outcomes

1. To analyze physiologic synchrony in GSR, first, an average slope of the GSR will be calculated in the patient and provider recordings in moving 5 second windows, offset by 1 second. Next, Pearson correlations with lag zero will be calculated over successive 15 second windows between time-locked patient and provider GSR slope values. Then, a single session index will be calculated from the ratio of the sum of the positive correlations across the entire visit divided by the sum of the absolute value of the negative correlations across the entire visit. To reduce skew, the natural logarithm of the index will be calculated. Thus, an index value of zero reflects equal positive and negative correlations, a value greater than zero reflects more concordance in GSR than not, while a value less than zero reflects less concordance in the dyad (less than 50%)⁸². These index values will be used in GLM analyses with GERD symptom severity and/or correlated with visit type.

We will also perform similar analyses on the HRV data – comparing variation in the beat-to-beat intervals over short segments of time and calculating Pearson correlation coefficients for time-locked patient and provider data for these intervals.

2. We will calculate absolute changes in both GSR and also high frequency HRV within study subjects from the beginning to the end of the study visit. We will assess the Pearson correlation between these changes and reported changes in GERD symptom severity. We will also look at absolute levels of GSR and HRV at the end of the study visit and compare those values with changes in GERD symptom severity in GLM models. As an exploratory analysis, I will test whether changes in GSR and HRV are a function of baseline perceived stress and if that relationship differs between the standard and expanded visit interventions.
3. To analyze study visit videos, 2 minute thin slices of each video at three time points (beginning, middle, and end of study visits) will be analyzed by trained and blinded coders, for the presence of 1) micro-level non-verbal supportive behaviors (e.g., gazes, smiles, nods, gestures – measured as absolute number or

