length of time) as well as 2) macro-level impression ratings of the interaction (e.g., engagement, friendliness, relaxed, empathic, reciprocity – measured on a 1-9 scale). The PI will meet weekly with the coders to review findings and resolve areas of disagreement until greater than 70% concordance is achieved between coders using Cronbach's alpha. Each of these variables will be assessed in a GLM examining time, visit type, and time x visit type effects. We will also calculate the Pearson correlation coefficient for each variable relative to improvement in GERD symptoms and construct a GLM examining patient and provider smiling as a predictor of improvement in GERD symptoms. Other models may also be constructed based on the results of the initial video analyses.

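### A PI who is not masked to visit type meets the video coders to resolve disagreements, and the plan does not keep the analysed ratings clear of that step

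*Combined protocol and SAP*

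**What the plan says.** Secondary outcome 3 (Sections 3 and 9.1) is a comparison of blinded ratings of two-minute video slices between visit types, together with their correlation with later symptom change. Secondary hypothesis 4 in Section 9.1 also depends on blinded review of the slices.

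Section 9.5.2 takes slices from the beginning, middle and end of each visit, which "will be analyzed by trained and blinded coders". Two kinds of measure result: counts or durations of behaviours such as gazes, smiles and nods, and overall impressions scored from 1 to 9.

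The coding is controlled as follows: "The PI will meet weekly with the coders to review findings and resolve areas of disagreement". The same sentence gives an end point: the meetings run until the coders exceed 70% concordance, judged by Cronbach's alpha. The next sentence takes each variable into a GLM with time, visit type and their interaction.

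On masking, Section 3 says that "study providers and the research team will know what the subject is receiving but the subject will not". Section 6.2.4 agrees: "Study providers and staff will be aware of the study intervention delivered, but only immediately prior to the study visit". On the PI in particular, Section 5.1 says: "The study PI will review video recordings of the interactions to offer feedback to study providers and ensure protocol fidelity". Section 9.4 adds: "The study PI will periodically review video recordings of visit interventions as the study progresses".

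**The concern.** The person who resolves coder disagreements knows which script was used and holds the hypothesis under test. Disagreements arise on the ambiguous slices, where an expectation about the visit type has most room to act. If study slices are discussed in these meetings and the scores that come out are analysed, the comparison between visit types no longer rests on masked judgement alone.

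At stake is hypothesis 4, that providers behave more supportively in expanded visits. The planned correlations of the ratings with symptom improvement, including hypothesis 5 on smiling, use the same coded data. Sections 10.2 and 10.3.3 also have the PI reviewing questionnaire data at least every 1-2 months, so the PI may know something of symptom response as well as visit type.

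The reliability figure has a related weakness. If agreement is computed after PI-led discussion, passing the threshold does not show that the coders agreed independently.

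**Working it through.** The plan gives no figure on this point, so the check is mainly a comparison of sections.

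**1. Is the PI masked to visit type?** No. Section 3 unmasks the research team, and Section 6.2.4 does the same for staff once the visit begins. The PI's review of recordings (5.1, 9.4, 10.3.3) leads to the same place: a reviewer who checks fidelity to one of two scripts must know which script applies. Section 9.3 confirms that the recordings show the visit type: "The actual intervention received will also be verified by reviewing study video recordings".

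**2. Are the ratings meant to be masked?** Yes. Sections 3 and 9.1 define the outcome that way, and Section 9.5.2 describes the coders that way. What the coders are masked to (visit type, symptom outcome, hypotheses) is not stated.

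**3. Where do the two meet?** In the weekly meeting in Section 9.5.2. Its stated subject is findings and disagreements. It stands between the description of coding each study video and the GLM by visit type.

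**4. Is there a safeguard?**

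| Possible safeguard | In the plan? |
|---|---|
| PI masked during the meetings | Not stated |
| Meetings limited to slices outside the analysis | Not stated |
| Independent pre-discussion ratings locked and analysed | Not stated |
| Masked third person adjudicates | Not stated |
| Stopping rule (over 70% concordance) | Stated; it limits how long the meetings run, not which slices they cover |
| General promise of masked data analysis (6.2.4) | Stated; it concerns analysis and does not mask someone who already knows the visit type |

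**5. Which measures are exposed?** Mainly the 1-9 impressions, because they are judgements. Counts and durations leave less room for an adjudicator. Hypothesis 4 uses both kinds; hypothesis 5, on smiling, uses the less exposed kind. The primary outcome is the subject's own diary (9.1, 9.5.1) and does not pass through this step.

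**6. Can the size be derived?** No. The documents give neither the share of ratings that would be disputed, nor how far discussion would move them, nor the SD of the 1-9 scale. The 70% threshold is tied to Cronbach's alpha, which is not a percentage of agreement, so it cannot be read as 30% of slices disputed.

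The following is therefore an illustration only. Assume one rating per subject, 30 per group (Section 9.2), no true difference, and a share *f* of ratings resolved with a net between-arm shift of *b* SD, always in the same direction. Then:

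- bias = *f* × *b* SD
- noncentrality = bias / √(2/30) = bias / 0.258
- the rejection rate is that of a two-sided t test at 0.05 with 58 degrees of freedom

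| *f* | *b* = 0.25 | *b* = 0.5 | *b* = 1.0 |
|---|---|---|---|
| 0.1 | 5.1% | 5.4% | 6.7% |
| 0.2 | 5.4% | 6.7% | 11.9% |
| 0.3 | 5.9% | 8.8% | 20.8% |

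For example, 0.2 × 0.5 = 0.10 SD, noncentrality 0.10 / 0.258 = 0.39, rejection rate 6.7%. The range runs from negligible to serious, and nothing in the plan says where within it the trial would lie.

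**The case against.** The strongest reply is that the sentence in Section 9.5.2 describes calibration. It ends with a reliability threshold, and meeting until coders agree well enough is ordinary coder training. If PI-settled scores replaced the coders' own, agreement would follow by construction and the threshold would mean little. Resolving disagreement may also mean clarifying coding definitions. Section 6.2.4 promises masked analysis.

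Much of this stands. Calibration is a reasonable reading, and these stronger inferences that a reader might draw are not supported:

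- *The PI sets or overrides the analysed scores.* No section says so.
- *The video outcome is unblinded.* The coders are described as masked, and nothing says that the PI tells them the visit type. They may well be masked when they first rate.
- *The PI has watched every visit in full.* Sections 5.1, 9.4 and 10.3.3 describe review of recordings, periodic in part. The point does not need this claim, since Section 3 already unmasks the research team.
- *A definite number of scale points is added to the difference.* Any such number would be an assumption multiplied out.

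The reply does not remove the gap. Calibration on study slices, led by someone who knows the visit type and the hypothesis, can still shape ratings that are later analysed. The plan does not say that such slices are left out or rated afresh. The promise in Section 6.2.4 does not reach the coding step.

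**Conclusion.** The concern holds in a limited form. The plan states a procedure by which an unmasked PI can influence ratings it calls blinded, and it contains no provision that prevents this. Whether the influence would reach the analysed scores depends on two things left open: whether the meetings use study slices, and which ratings enter the GLM. The conclusion rests on the PI being part of the research team that Section 3 unmasks, which the PI's review of recordings supports.

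The effect is confined to secondary outcome 3 and secondary hypotheses 4 and 5, and mainly to the 1-9 impressions. The primary analysis is not affected. The size of any bias is unknown. The change is worth making because it is cheap and protects a property that the plan itself relies on.

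**What to change.** Amend Section 9.5.2 to say that:

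- PI-led meetings are for calibration only and use training slices outside the analysis set;
- for study slices, each coder's independent rating is locked before any discussion, agreement is computed on these locked ratings, and their mean is analysed;
- any consensus step on study slices is left to the masked coders, without the PI;
- the coders are masked to named items, such as visit type, symptom outcome and hypotheses.

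The section should also say whether every study slice is rated by more than one coder, since the agreement figure and the mean both depend on it.

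The cost is wording, plus a few slices or other recordings set aside for training. No extra staff are needed for the change to the meetings. If the intention was calibration all along, the first two items simply put it on record.

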1. Ratio of the sum of positive correlations over the sum of negative correlations in GSR (or HRV) across patient-provider encounters for standard vs. expanded visit types and for responders vs. non-responders (those with a 50% or greater improvement in their GERD symptom severity).
2. Absolute change in GSR (or high frequency HRV signal) in patient recordings from the beginning of the study visit to the end of the study visit and correlation with subsequent change in GERD symptom severity.
3. Differences in blinded ratings of 2 minute thin slices of study visit videos from the beginning to the end of the study in supportive global impressions (e.g., engagement, relaxed, patient seems pleased/satisfied) and non-verbal behaviors (e.g., smiling) between standard and expanded visit types and correlation with subsequent change in GERD symptom severity.

Validity and reliability of outcome measures:

1. Assessment of physiologic concordance has been described by a number of groups and we will be using similar methodology^{45,82}.
2. GERD symptom severity will be assessed by a daily symptom diary used by a number of other groups in medication trials and in our previous study^{64,83,84}. The average daily GERD symptom severity is based on the daily sum of scores from the first three questions assessing severity of daytime heartburn, nighttime heartburn, and acid reflux averaged over a 7 day period. The change in GERD symptom severity is calculated by subtracting the average daily GERD symptom severity score during the last 7 days of the study from the average daily GERD symptom severity score at study enrollment. The other GERD symptom questionnaires we are using have also been validated^{26,73,74}.
3. Social psychologists have developed and validated a variety of coding schemes to analyze providers' verbal and non-verbal behaviors and to link these behaviors with patient satisfaction, understanding, trust, rapport, empathy, and a variety of related factors^{9,58-63}. We will use a subset of these validated coding

schemes. Thin slices have shown high reliability and validity for behaviors such as gaze, nods, and smiles⁸⁵.

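### The video-coder acceptance rule uses Cronbach's alpha as if it were agreement; it can pass coders with a systematic offset, and the harm depends on a coding design the plan does not state

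*Combined protocol and SAP*

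**What the plan says.** Section 9.5.2, item 3, describes the video coding. Two-minute excerpts from the start, middle and end of each visit "will be analyzed by trained and blinded coders". Supportive behaviours such as gazes and smiles are recorded as counts or durations, and overall impressions are "measured on a 1-9 scale". The principal investigator meets the coders each week to settle differences "until greater than 70% concordance is achieved between coders", and the statistic named for this is Cronbach's alpha.

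The resulting variables then go into the analysis: "Each of these variables will be assessed in a GLM examining time, visit type, and time x visit type effects". Each is also correlated with improvement in GERD symptoms, and smiling is modelled as a predictor of that improvement. These analyses serve secondary outcome 3 and secondary hypotheses 4 and 5 in Section 9.1.

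The only other statement on reliability of the coding is in Section 9.1, and it is a general one from the literature: "Thin slices have shown high reliability and validity for behaviors such as gaze, nods, and smiles". The documents name no ICC, kappa or percent-agreement criterion. They do not give the number of coders. They also do not say whether every coder rates every slice, whether scores are averaged, or whether the threshold applies to each variable separately.

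**The concern.** The rule joins two different quantities. Concordance of 70% describes how often coders give the same answer. Alpha of 0.70 describes how consistently coders rank slices once their scores are summed. Alpha is unchanged if one coder always scores higher than another by a fixed amount, and for a given inter-coder correlation it rises as coders are added. Meeting the rule therefore does not show that two coders would give the same slice the same rating or count.

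This matters if the analysed value for a slice comes from one coder. An offset between coders then becomes extra variation between slices, or between visits, that the acceptance check cannot see. Low single-coder reliability would also weaken the planned correlations with GERD improvement, in a trial of 60 subjects. The weekly meetings end when the alpha criterion is met, so an offset that passes alpha need not be resolved.

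**Working it through.** The 70% is a chosen threshold, so there is no derived figure to reproduce. The check is what the threshold guarantees.

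**Inputs.** From Section 9.5.2: the threshold, read as alpha above 0.70; the 1-9 scale; counts or durations for behaviours. Assumed, because not stated: the number of coders k, shown for 2 to 4. The rating patterns below are constructed and are not data from the trial.

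**1. Alpha and a constant offset.** Treat coders as items:

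alpha = k/(k-1) × (1 - sum of coder variances / variance of coder totals).

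Let coder B always score d points above coder A, and let s² be the variance of A's ratings. Each coder has variance s² and the total has variance 4s², so alpha = 2 × (1 - 2s²/4s²) = 1.00 for any d. Exact agreement is 0% for any d other than 0. With no residual error, the two-way absolute-agreement ICCs for two coders reduce (large-sample form) to:

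- single measure: s²/(s² + d²/2)
- average measure: s²/(s² + d²/4)

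A's ratings are spread evenly over the range shown, so that s² = (m² - 1)/12 for ratings 1 to m.

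| Gap d | A's range | s² | Alpha | Exact agreement | Single-measure ICC |
|---|---|---|---|---|---|
| 1 | 1-7 | 4.00 | 1.00 | 0% | 4/4.5 = 0.89 |
| 2 | 1-7 | 4.00 | 1.00 | 0% | 4/6 = 0.67 |
| 3 | 1-6 | 2.92 | 1.00 | 0% | 2.92/7.42 = 0.39 |
| 4 | 1-5 | 2.00 | 1.00 | 0% | 2/10 = 0.20 |

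If B instead always scores double A (1-4 against 2-8), alpha is 0.89, exact agreement 0% and the single-measure ICC 0.40.

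**2. What alpha of 0.70 implies for one coder.** Inverting Spearman-Brown, mean r = alpha/(k - alpha(k-1)):

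- k = 2: 0.70/1.30 = 0.54
- k = 3: 0.70/1.60 = 0.44
- k = 4: 0.70/1.90 = 0.37

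In simulated ratings from two unbiased coders at r = 0.54 (mean 5, SD 1 to 2, rounded to 1-9), exact agreement was about 38% down to 21%. Alpha after rounding was 0.66 to 0.69, just under the threshold. So alpha near 0.70 is far from 70% agreement even without an offset.

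**3. The reverse case.** Take 60 slices on which both coders score 5 in 54, and in the other 6 one scores 5 and the other 6 (3 each way). Agreement is 90% and alpha is -0.11. An ICC would also be low here, because the slices hardly vary. This shows that alpha is not a percentage. It is not a point in favour of the ICC.

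**4. Effect on the planned correlations.** With coder error in the video variable only, the true correlation is multiplied by the square root of the reliability of the score analysed:

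- one coder's score, alpha 0.70 from 2 coders: √0.538 = 0.73
- mean of all coders, alpha 0.70: √0.70 = 0.84, for any number of coders

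**The case against.** The strongest reply is that alpha is the right statistic for one sensible design. With coders as items, it equals the consistency ICC of the coder average. If every coder rates every slice and the mean is analysed, a constant offset adds the same amount to every slice. It then drops out of the visit-type, time and interaction contrasts and out of the Pearson correlations. In that design it is also correct that alpha rises with more coders, because the mean is then more reliable. All of this stands. But the plan states neither full overlap nor averaging, so the reply cannot be taken as settled.

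Safeguards exist: coders are trained and blinded, and disagreements are reviewed weekly. A large constant gap might well be noticed in those meetings. This lowers the likelihood of the problem, but the stated stopping criterion does not require a gap to be closed. If alpha is computed after discussion, it will also overstate independent reliability, and the text does not say which ratings are used.

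An absolute-agreement ICC is not perfect either. At a threshold of 0.70, the single-measure form still passes the constant 1-point gap (0.89).

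A reader might infer that the rule does pass coders who never agree, or that the comparison between visit types is biased. The documents support neither. Section 1 of the working shows a possibility, and nothing in the protocol suggests that a 3-point gap is likely. With blinded coders, a remaining offset mainly adds noise. Bias would need coders to be unevenly spread across visit types or time points.

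**Conclusion.** The point holds in conditional form. The plan sets a specific acceptance rule, names a statistic that does not measure what the rule describes, and supplies no other agreement measure. The rule can pass coders with a systematic offset, and alpha of 0.70 guarantees a mean inter-coder correlation of only 0.54, 0.44 or 0.37 with 2, 3 or 4 coders.

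The cost depends on the coding design. With single-coder scores or divided slices, an offset is undetected error and, with 2 coders, correlations are multiplied by about 0.73. With full overlap and averaging, the offset cancels and the factor is 0.84; the fault is then mostly one of wording. It would be wrong to quote 0.73 as the loss in this trial, since the analysed score is not specified.

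These figures assume coders with equal variances and reliabilities, and the offset examples are constructed. The reach is limited to secondary outcome 3 and hypotheses 4 and 5. The primary outcome is a patient diary score analysed by ANCOVA and is untouched. The change is worth making before coding starts, because ratings already revised in discussion cannot later be made independent.

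**What to change.** In Section 9.5.2, drop the wording about 70% concordance and replace alpha with a two-way absolute-agreement ICC, reported for each variable (counts, durations and 1-9 ratings). Compute it on independent ratings made before the weekly discussion, and apply the 0.70 threshold to that ICC.

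State the number of coders, which slices are rated by more than one coder, and which score enters the analysis. Use the single-measure ICC if one coder's score is analysed, and the average-measure ICC if the mean of coders who all rate the slice is analysed. Analyse the mean wherever slices are multiply coded. The form matters: for the constant 2-point gap the average-measure ICC is 4/(4 + 1) = 0.80, which passes, while the single-measure value of 0.67 does not. That is acceptable, because the gap cancels when the mean is analysed.

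The cost is a change of SAP wording, possibly somewhat longer coder training, and the need to keep the pre-discussion ratings. If little double coding is planned at present, some extra coding is needed to estimate the ICC.
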